Descriptive statistics (means, SD, and frequencies) will be calculated and Q-Q plots of residuals used to test for normality and skewness. Significance will be set at $P<0.05$. Data with a time component will be analyzed using a linear mixed effects model with subjects as a random factor and condition and time as fixed factors using SAS. Main effects of condition and condition X time interactions will be probed with planned comparisons to examine differences between β -OHB and placebo at each time point. Data with skewed distributions will be log-transformed or non-linear mixed effects models will be used. All participants will be included in the intention-to-treat (ITT) analyses and missing data will not be imputed, per contemporary guidelines with use of linear mixed models [16].

Sample Size

Twenty participants will be included in this cross-over study. In our pilot study on healthy volunteers we saw a ~15% reduction in glucose area under the curve after

ketone supplementation versus placebo. Using means and standard deviations from our previously published study in people with T2D (N=51) [17] for fasting glucose (8.6 +/- 2.3) a 15% reduction in blood glucose corresponds to an effect size $d = 0.73$. Assuming 80% power with an alpha level of 0.05 and a moderate correlation between repeated measures of $r=0.7$ (calculated using G*Power v3.1) a total sample size of $n=14$ is needed to detect differences between ketone and placebo conditions. To preserve power and account for any dropouts or missing blood samples we will recruit 20 participants, aiming for equal males and females.[2][17]

Significance

The results of this study will help determine whether supplementation with exogenous ketones can alter metabolism and subsequently improve blood glucose levels. This is a pilot study and it will provide useful data to better answer future research questions and aid in the design of longer term studies.

OUTCOMES MEASUREMENTS AND METHODS

The primary outcome measure is the plasma glucose concentrations over the 3-hour period following the ingestion of the beverages. Secondary measures will include plasma insulin and C-peptide, free fatty acids, inflammatory cytokines, CBF, cognitive function and neurovascular coupling, inflammation signalling molecules, appetite/satiety levels and gastrointestinal distress questionnaire.

Anthropometric Measures

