The effect of acute exogenous oral ketone supplementation on blood glucose levels in type 2 diabetes

NCT 04194450

Version 7 – April 2, 2022 [H19-02947]

STATISTICAL ANALYSIS PLAN (SAP)

Exogenous Ketones in Type 2 Diabetes

Trial Registration: NCT04194450

Version 1: November 8, 2021 with dated adjustments up to April 2, 2022.

BACKGROUND AND AIM:

From December 2019 to November 2021, we completed the randomized crossover placebo-controlled study titled “Exogenous Ketones in Type 2 Diabetes”. The aim of the trial was to determine whether acutely ingesting exogenous ketones, in the form of a ketone monoester drink (0.3 g/kg (R)-3-hydroxybutyl (R)-3-hydroxybutyrate, Δ G®, TDeltaS, Oxford, UK, provided by HVMN), can lower blood glucose in individuals with type 2 diabetes (T2D). The trial also aimed to examine the impact of exogenous ketones on brain/cognitive function, measures of inflammation, and appetite. The primary outcome was plasma glucose concentration after consumption of exogenous ketones compared to ingestion of placebo assessed over 180 minutes following supplement consumption. It was hypothesized that consumption of exogenous ketones would lower blood glucose compared to the placebo.

SAMPLE SIZE CONSIDERATIONS

At the time of study design, there were no known studies evaluating the effect of acute supplementation with exogenous ketones in individuals with T2D. Therefore, we estimated sample size based on our pilot study in healthy volunteers, in which we saw a \sim 15% reduction in glucose area under the curve after ketone supplementation compared to placebo [1]. Using means and standard deviations for fasting glucose (8.6 ± 2.3 mM) from our previously published study in people with T2D ($N = 51$) [2], a 15% reduction in blood glucose corresponds to an effect size of $d = 0.73$. Assuming 80% power with an alpha level of 0.05 and a moderate correlation between repeated measures of $r = 0.7$, a total sample size of $N = 14$ is needed to detect differences between ketone and placebo conditions (calculated using G*Power v3.1). To preserve power

and account for any dropouts or missing blood samples, we aimed to recruit 20 participants, aiming for equal males and females.

ANALYSIS SET AND STUDY POPULATION

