The full analysis set of data will be derived from the set of all randomized participants in an intention-to-treat (ITT) analysis. All outliers that are within the realm of biological plausibility will be included in the analysis and only obvious data errors (e.g., resulting from technical issues) will be excluded. No statistical imputations will replace missing data for the outcome measures (*data as observed*), per contemporary guidelines [3]. However, the linear mixed effects model (see below for further details) is a principled approach to addressing missing outcome data. The model permits the inclusion of all participants in the analysis with a follow-up value (regardless of missing timepoints within a condition, or a missing alternative condition). Statistical analysis will be performed blinded to participant allocation.

OUTCOMES, STATISTICAL METHODS, AND COVARIATES

Primary endpoint: The preregistered primary outcome for this trial will be a comparison of blood glucose values assessed over 180 minutes following consumption of exogenous ketones or a placebo. Data will be analyzed according to the ITT principle via a linear mixed effects model with fixed effects for time after supplement ingestion (i.e., 30, 60, 90, 120, 150, 180 minutes), condition (i.e., ketone monoester vs placebo), period (depending on which condition was conducted first), and an interaction between time and condition and time and period as well as the baseline value (assessed at “time 0” immediately before consumption of the supplement) as a covariate. A random intercept for each participant (ID) and a random slope for time on the interaction of ID and period will be included. If a participant has a baseline value missing, we will impute this as the average (mean) baseline value observed across participants. Model assumptions of normality and linearity will be assessed visually by inspecting a Q-Q plot, and homoscedasticity will be assessed by plotting residuals vs fitted values. Models will be run using log-transformed outcome variables when departure from model assumptions is observed.

In addition to the primary analysis detailed above, we will explore the primary endpoint via the following confirmatory analyses:

1. Paired t-test on blood glucose incremental area under the curve (i.e., glucose above baseline fasting values across 180 minutes after ingestion of supplement or placebo)

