2. Paired t-test on peak blood glucose concentration (i.e., highest blood glucose value measured after ingestion of supplement or placebo)
3. Paired t-test on peak blood glucose concentration above baseline (i.e., highest blood glucose value above fasting baseline after ingestion of supplement or placebo)
4. Paired t-test on blood glucose total area under the curve (i.e., glucose above zero across 180 minutes after ingestion of supplement or placebo)

Secondary outcome measures:

Secondary outcomes will be analyzed similarly to the primary outcome using a linear mixed effects model. Secondary and exploratory blood marker outcomes that are below or above the detection limit, will be imputed as limit of detection (LOD) / $\sqrt{2}$ or $LOD * \sqrt{2}$, respectively [4]. Preregistered secondary outcomes include:

1. Metabolic outcomes (plasma insulin, plasma c-peptide, plasma free fatty acids, plasma β -OHB)
2. Markers of brain/cognitive function (intracranial blood flow measured by ultrasound, blood pressure measured manually, cognitive function using BrainBaseline on an iPad, brain-derived neurotrophic factor)
3. Markers of inflammation (plasma tumour necrosis factor alpha, plasma interleukin-1 β , plasma interleukin-6, total blood monocytes and monocyte subsets, monocyte histone acetylation)
4. Markers of appetite (self-reported hunger and fullness assessed via a 0 to 100 mm Visual Analog Scale, gastrointestinal symptoms assessed via a 0 to 100 mm Visual Analog Scale, total energy consumed in kilocalories during a buffet style meal at the end of testing)

Exploratory outcomes measures:

Exploratory outcomes will be analyzed similarly to the primary outcome using a linear mixed effects model.

Exploratory outcomes that were not preregistered include:

1. Metabolomics
2. Electrolyte status, lactate, pH etc.

REPORTING RESULTS

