We will summarize data (including participant baseline characteristics) as mean \pm standard deviation (SD) for continuous and N (%) for categorical data. A significant effect will be concluded at two-sided P -value of < 0.05 . We will report on the effect of condition and the interaction of the treatment effect over time. Effect estimates from the model alongside 95% confidence intervals around the mean differences in the outcome after accounting for the included covariates will be reported. Changes in outcome within condition (e.g., effect of ketone monoester on blood glucose at 180 minutes compared to baseline) will be reported via mean differences with SD outside the model, if applicable. Effect sizes (Hedges' g) will be stated.

PROGRAMMING PLAN

Statistical analysis will be performed after the last patient out, using R [5].

REFERENCES

1. Myette-Côté, É., et al., Prior ingestion of exogenous ketone monoester attenuates the glycaemic response to an oral glucose tolerance test in healthy young individuals. *The Journal of Physiology*, 2018. **596**(8): p. 1385-1395.
2. Francois, M.E., et al., Combined interval training and post-exercise nutrition in type 2 diabetes: a randomized control trial. *Frontiers in Physiology*, 2017. **8**: p. 528.
3. Chakraborty H. A mixed model approach for intent-to-treat analysis in longitudinal clinical trials with missing values [Internet]. 2009. Available at: <http://www.rti.org/publication/mixed-model->

approach-intent-treat-analysis-longitudinal-clinical-trials-missing-values

4. Canales R.A., et al. Methods for handling left-censored data in quantitative microbial risk assessment. *Appl Environ Microbiol* 2018. **84**(20): e01203-18.
5. Team RC. A Language and Environment for Statistical Computing. R Foundation for Statistical Computing 2020. Available at (accessed November 4, 2021): <https://www.r-project.org/>
- 6.

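### The stated requirement of 14 participants does not give 80% power under the SAP's two-sided rule; the plan's own inputs need 17 complete pairs, which the planned 20 still covers

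*Protocol*

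**What the plan says.** The protocol (Sample Size) takes a fasting glucose of 8.6 with SD 2.3 from an earlier study in people with T2D. It equates a 15% reduction with an effect size of d = 0.73. "Assuming 80% power with an alpha level of 0.05" and a correlation of 0.7 between repeated measures, it concludes that "a total sample size of $n=14$ is needed to detect differences between ketone and placebo conditions". It names G\*Power v3.1 as the software and sets recruitment at 20 to cover dropouts and missing blood samples. The SAP (Sample Size Considerations) restates the same inputs, the same 14 and the same 20.

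Neither sample-size text gives the sidedness. The protocol's Statistical Analyses section gives only a 0.05 threshold. The SAP (Reporting Results) is explicit: "A significant effect will be concluded at two-sided" P below 0.05.

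The SAP's primary analysis is a linear mixed model. It also lists four supporting paired t-tests, among them "Paired t-test on blood glucose total area under the curve".

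**The concern.** A power statement should refer to the test that will be used to claim an effect. Here the SAP restates 14 as sufficient for 80% power and later commits to a two-sided test, and 14 looks too small for that test at an effect size of 0.73.

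Two things depend on the figure. The first is the power claim itself, which a report of the trial would probably repeat. The second is the margin in the recruitment target. A reader who sees 14 needed and 20 recruited infers that six participants can be lost before power falls below 80%. The protocol also calls this a pilot intended to help design longer studies, so a one-sided figure carried forward as two-sided would make those studies too small.

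**Working it through.** **Inputs**, all from the protocol's Sample Size section and repeated in the SAP: mean 8.6 mmol/L, SD 2.3, reduction 15%, correlation r = 0.7, alpha 0.05, power 80%. Sidedness comes from the SAP's Reporting Results section. Equal SD in the two conditions is my assumption, because only one SD is given.

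**Step 1: what d = 0.73 is.**

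- Difference: 0.15 × 8.6 = 1.29 mmol/L.
- Standardised by the between-person SD: 1.29 / 2.3 = 0.56. This is not 0.73.
- SD of within-person differences: 2.3 × √(2 × (1 − 0.7)) = 2.3 × √0.6 = 1.78.
- Paired effect size: dz = 1.29 / 1.78 = 0.724. If 1.29 is rounded to 1.3, dz = 0.730.

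The stated 0.73 is therefore the paired effect size with r = 0.7 already in it. I carry both 0.724 and 0.73 forward.

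**Step 2: reproduce the stated 14.** Power for a paired t-test with n pairs comes from the noncentral t distribution with n − 1 degrees of freedom and noncentrality dz × √n. The smallest n reaching 80% under each reading is:

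| Reading | n |
|---|---|
| Paired t, one-sided 0.05 | 14 |
| Paired t, two-sided 0.05 | 17 |
| Two-sided normal approximation (14.73 to 14.97) | 15 |
| r = 0.7 applied a second time to 0.73 (dz = 0.942) | 11 two-sided, 9 one-sided |
| 0.56 with no correlation | 27 two-sided, 22 one-sided |
| Repeated-measures ANOVA, two measures, f = 0.365 or f = 0.28 | 11 or 18 |
| Two independent groups, d = 0.73 | 30 per group |

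Of these, only the one-sided paired t-test gives exactly 14. It has 79.2–79.8% power at 13 pairs and 82.1–82.7% at 14.

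**Step 3: power under the two-sided rule.**

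| Complete pairs | Power at dz 0.724 | Power at dz 0.73 |
|---|---|---|
| 14 | 70.7% | 71.4% |
| 15 | 74.2% | 74.8% |
| 16 | 77.3% | 77.9% |
| 17 | 80.0% | 80.7% |
| 20 | 86.7% | 87.2% |

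**Step 4: what would make 14 correct two-sided.** Solving for 80% power at 14 pairs gives dz = 0.810. At r = 0.7 that is 0.810 × 1.78 = 1.44 mmol/L, a 16.8% reduction instead of 15%. With the reduction held at 15%, it needs r = 0.76 instead of 0.7.

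**Step 5: allowing for a period effect.** With n − 2 degrees of freedom, 17 pairs give 79.7–80.3% and 20 pairs give 86.5–87.0%. The picture does not change.

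**The case against.** The best defence is that 14 is not a miscalculation. It is the correct answer for a one-sided paired t-test, the hypothesis is directional in both documents, and the protocol never says two-sided. The two-sided rule appears only in the SAP, whose first version is dated November 2021, the month in which it says the study was completed. This may well explain where 14 came from. It does not remove the mismatch, because the SAP itself gives 14 for 80% power and also adopts the two-sided rule.

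A second point is that no decision depends on the figure: 20 exceeds 17 and the trial is over. That is true, and it limits the seriousness. The power claim still stands uncorrected in both documents.

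Third, neither 71% nor 87% is the power of the primary analysis. This stands. The mixed model adjusts for baseline and period and retains participants "regardless of missing timepoints within a condition, or a missing alternative condition", and its power cannot be derived from the stated inputs. The figures here apply to a paired comparison of complete pairs. That is what the plan's calculation describes, and what the SAP's total-AUC t-test performs.

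Fourth, 17 depends on equal SDs. If the SD fell in proportion to the mean (2.3 to 1.955, an assumption not in the documents), dz would be 0.769. Then 16 pairs would suffice and 14 would give about 76%, still short of 80%.

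Finally, the documents give no dropout rate and do not promise a reserve of six. The six is simply 20 − 14.

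**Conclusion.** The concern holds. On the plan's own inputs and the SAP's two-sided rule, the requirement is 17 complete pairs, not 14. At 14 pairs the power is about 71%, roughly 9 percentage points below the 80% claimed. The margin for a complete-pairs test is 20 − 17 = 3 participants, not 20 − 14 = 6.

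The planned 20 is not in question: it gives about 87% power if all 20 pairs are complete. The error lies in the stated justification, and it should be corrected although the trial's size is sound.

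The result rests on an exact paired t-test, equal SDs in the two conditions, and d = 0.73 being the paired effect size. The last is a strong inference from the arithmetic, but the documents do not say it. That the original run was one-sided is likely but not documented.

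**What to change.** Check the saved power output for the number of tails and the definition of d. Then issue a dated correction to the sample-size text of both documents that:

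- records the sidedness of the original calculation as the output shows it, and states that the corrected requirement is two-sided, to match the SAP's decision rule;
- defines d as the paired effect size (0.72–0.73), with r = 0.7 already included and equal SDs assumed;
- replaces 14 with 17 complete pairs for 80% power, and adds that 20 complete pairs give about 87%;
- says that these figures are for a paired t-test and not for the primary mixed model.

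The cost is a few sentences in each document. No participants are added and no analysis changes. The stated requirement becomes slightly less favourable.

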The effect of acute exogenous oral ketone supplementation on blood glucose levels in type 2 diabetes

NCT 04194450

Version 7 – April 2, 2022 [H19-02947]

STATISTICAL ANALYSIS PLAN (SAP)

Exogenous Ketones in Type 2 Diabetes

Trial Registration: NCT04194450

Version 1: November 8, 2021 with dated adjustments up to April 2, 2022.

BACKGROUND AND AIM:

From December 2019 to November 2021, we completed the randomized crossover placebo-controlled study titled “Exogenous Ketones in Type 2 Diabetes”. The aim of the trial was to determine whether acutely ingesting exogenous ketones, in the form of a ketone monoester drink (0.3 g/kg (R)-3-hydroxybutyl (R)-3-hydroxybutyrate, Δ G®, TDeltaS, Oxford, UK, provided by HVMN), can lower blood glucose in individuals with type 2 diabetes (T2D). The trial also aimed to examine the impact of exogenous ketones on brain/cognitive function, measures of inflammation, and appetite. The primary outcome was plasma glucose concentration after consumption of exogenous ketones compared to ingestion of placebo assessed over 180 minutes following supplement consumption. It was hypothesized that consumption of exogenous ketones would lower blood glucose compared to the placebo.

SAMPLE SIZE CONSIDERATIONS

At the time of study design, there were no known studies evaluating the effect of acute supplementation with exogenous ketones in individuals with T2D. Therefore, we estimated sample size based on our pilot study in healthy volunteers, in which we saw a \sim 15% reduction in glucose area under the curve after ketone supplementation compared to placebo [1]. Using means and standard deviations for fasting glucose (8.6 ± 2.3 mM) from our previously published study in people with T2D ($N = 51$) [2], a 15% reduction in blood glucose corresponds to an effect size of $d = 0.73$. Assuming 80% power with an alpha level of 0.05 and a moderate correlation between repeated measures of $r = 0.7$, a total sample size of $N = 14$ is needed to detect differences between ketone and placebo conditions (calculated using G*Power v3.1). To preserve power

and account for any dropouts or missing blood samples, we aimed to recruit 20 participants, aiming for equal males and females.

ANALYSIS SET AND STUDY POPULATION

The full analysis set of data will be derived from the set of all randomized participants in an intention-to-treat (ITT) analysis. All outliers that are within the realm of biological plausibility will be included in the analysis and only obvious data errors (e.g., resulting from technical issues) will be excluded. No statistical imputations will replace missing data for the outcome measures (*data as observed*), per contemporary guidelines [3]. However, the linear mixed effects model (see below for further details) is a principled approach to addressing missing outcome data. The model permits the inclusion of all participants in the analysis with a follow-up value (regardless of missing timepoints within a condition, or a missing alternative condition). Statistical analysis will be performed blinded to participant allocation.

OUTCOMES, STATISTICAL METHODS, AND COVARIATES

Primary endpoint: The preregistered primary outcome for this trial will be a comparison of blood glucose values assessed over 180 minutes following consumption of exogenous ketones or a placebo. Data will be analyzed according to the ITT principle via a linear mixed effects model with fixed effects for time after supplement ingestion (i.e., 30, 60, 90, 120, 150, 180 minutes), condition (i.e., ketone monoester vs placebo), period (depending on which condition was conducted first), and an interaction between time and condition and time and period as well as the baseline value (assessed at “time 0” immediately before consumption of the supplement) as a covariate. A random intercept for each participant (ID) and a random slope for time on the interaction of ID and period will be included. If a participant has a baseline value missing, we will impute this as the average (mean) baseline value observed across participants. Model assumptions of normality and linearity will be assessed visually by inspecting a Q-Q plot, and homoscedasticity will be assessed by plotting residuals vs fitted values. Models will be run using log-transformed outcome variables when departure from model assumptions is observed.

In addition to the primary analysis detailed above, we will explore the primary endpoint via the following confirmatory analyses:

1. Paired t-test on blood glucose incremental area under the curve (i.e., glucose above baseline fasting values across 180 minutes after ingestion of supplement or placebo)
2. Paired t-test on peak blood glucose concentration (i.e., highest blood glucose value measured after ingestion of supplement or placebo)
3. Paired t-test on peak blood glucose concentration above baseline (i.e., highest blood glucose value above fasting baseline after ingestion of supplement or placebo)
4. Paired t-test on blood glucose total area under the curve (i.e., glucose above zero across 180 minutes after ingestion of supplement or placebo)

Secondary outcome measures:

Secondary outcomes will be analyzed similarly to the primary outcome using a linear mixed effects model. Secondary and exploratory blood marker outcomes that are below or above the detection limit, will be imputed as limit of detection (LOD) / $\sqrt{2}$ or $LOD * \sqrt{2}$, respectively [4]. Preregistered secondary outcomes include:

1. Metabolic outcomes (plasma insulin, plasma c-peptide, plasma free fatty acids, plasma β -OHB)
2. Markers of brain/cognitive function (intracranial blood flow measured by ultrasound, blood pressure measured manually, cognitive function using BrainBaseline on an iPad, brain-derived neurotrophic factor)
3. Markers of inflammation (plasma tumour necrosis factor alpha, plasma interleukin-1 β , plasma interleukin-6, total blood monocytes and monocyte subsets, monocyte histone acetylation)
4. Markers of appetite (self-reported hunger and fullness assessed via a 0 to 100 mm Visual Analog Scale, gastrointestinal symptoms assessed via a 0 to 100 mm Visual Analog Scale, total energy consumed in kilocalories during a buffet style meal at the end of testing)

Exploratory outcomes measures:

Exploratory outcomes will be analyzed similarly to the primary outcome using a linear mixed effects model.

Exploratory outcomes that were not preregistered include:

1. Metabolomics
2. Electrolyte status, lactate, pH etc.

REPORTING RESULTS

We will summarize data (including participant baseline characteristics) as mean \pm standard deviation (SD) for continuous and N (%) for categorical data. A significant effect will be concluded at two-sided P -value of < 0.05 . We will report on the effect of condition and the interaction of the treatment effect over time. Effect estimates from the model alongside 95% confidence intervals around the mean differences in the outcome after accounting for the included covariates will be reported. Changes in outcome within condition (e.g., effect of ketone monoester on blood glucose at 180 minutes compared to baseline) will be reported via mean differences with SD outside the model, if applicable. Effect sizes (Hedges' g) will be stated.

PROGRAMMING PLAN

Statistical analysis will be performed after the last patient out, using R [5].

REFERENCES

1. Myette-Côté, É., et al., Prior ingestion of exogenous ketone monoester attenuates the glycaemic response to an oral glucose tolerance test in healthy young individuals. *The Journal of Physiology*, 2018. **596**(8): p. 1385-1395.
2. Francois, M.E., et al., Combined interval training and post-exercise nutrition in type 2 diabetes: a randomized control trial. *Frontiers in Physiology*, 2017. **8**: p. 528.
3. Chakraborty H. A mixed model approach for intent-to-treat analysis in longitudinal clinical trials with missing values [Internet]. 2009. Available at: <http://www.rti.org/publication/mixed-model->

approach-intent-treat-analysis-longitudinal-clinical-trials-missing-values

4. Canales R.A., et al. Methods for handling left-censored data in quantitative microbial risk assessment. *Appl Environ Microbiol* 2018. **84**(20): e01203-18.
5. Team RC. A Language and Environment for Statistical Computing. R Foundation for Statistical Computing 2020. Available at (accessed November 4, 2021): <https://www.r-project.org/>
- 6.

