A randomized placebo-controlled, cross-over pilot study in which 20 adults with type 2 diabetes will participate in two experimental trials. All participants will provide written informed consent during an initial familiarization visit.

Following screening, eligible participants (N=20) will participate in two experimental trials of β -OHB supplementation versus placebo with order of treatment balanced, separated by ~7 days. Pre-menopausal women will be tested in the follicular phase (days 3-9) to minimize any potential changes in insulin sensitivity across the menstrual cycle [8]. Participants will be asked to refrain from structured exercise and alcohol, and limit physical activity to their activities of daily living on the day before each trial. A standardized diet with ~50% energy from carbohydrate, ~30% fat, ~20% protein (energy based on Harris-Benedict equation with an activity factor of 1.4) will be oriented on the day before each trial. Participants will then fast overnight (8-10h) and refrain from taking any medications 24 hours before the morning of the trial. Upon arrival, an indwelling intravenous catheter will be inserted and a baseline fasting blood sample will be obtained. The oral β -OHB supplement or placebo will be consumed in liquid form (~20-25 mL). Both drinks are masked with a proprietary calorie-free strawberry flavour developed by H.V.M.N®, USA, which results in the same taste profile for each. The β -OHB supplement will provide 0.3 g/kg β -OHB in the form of the ketone monoester (*R*)-3-hydroxybutyl (*R*)-3-hydroxybutyrate (Δ G®, TDeltaS, Oxford, UK). We used this dose in our supporting pilot study and published work shows it can consistently raise blood β -OHB levels to ~2-3 mmol/L within 15-30 minute[9] [2] [10]. Post consumption of the β -OHB or placebo blood samples will be obtained at 30, 60, 90, 120, 150 and 180 minutes.

The primary outcomes will be total plasma glucose as represented by the 3-hour area under the curve. Secondary outcomes include plasma insulin and C-peptide levels, plasma free fatty acids (FFA), inflammatory cytokines, cerebral blood flow (CBF), cognitive function, BDNF, signalling molecules, self reported hunger and fullness by a Visual Analog Scale (VAS) and GI symptom questionnaire scores – all measured across 180 minutes post-supplementation.

Metabolite and hormone analyses

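### The AUC and peak glucose analyses are paired t-tests that lack the missing-data and period protections of the primary mixed model

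*SAP*

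**What the plan says.** The SAP's section on the analysis set rules out imputing outcomes: "No statistical imputations will replace missing data for the outcome measures". It then explains that the mixed model can include participants "regardless of missing timepoints within a condition, or a missing alternative condition". That explanation concerns the model only.

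The primary endpoint section adds fixed effects for period and for time by period to that model, with the baseline value as a covariate. It continues: "we will explore the primary endpoint via the following confirmatory analyses". Four paired t-tests follow:

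- "Paired t-test on blood glucose incremental area under the curve" (analysis 1)
- "Paired t-test on peak blood glucose concentration" (analysis 2), and the same for peak above baseline (analysis 3)
- "Paired t-test on blood glucose total area under the curve" (analysis 4)

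Both areas are defined over the full 180 minutes. None of the four tests has a period term, and none has a rule for an incomplete profile. The mean-baseline rule is written for the model's covariate and is not extended to incremental AUC or peak above baseline.

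The sample size section expects losses: 20 were to be recruited partly to "account for any dropouts or missing blood samples".

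The documents differ on the primary outcome. The protocol's experimental design section gives "total plasma glucose as represented by the 3-hour area under the curve". The protocol's outcomes section and the SAP give glucose concentrations over the 3 hours.

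**The concern.** Leaving missing values unfilled is sound for a likelihood-based mixed model, which uses each observed sample where it falls. An AUC or a peak is instead built from the whole profile before any test is run. With no imputation, a visit that lacks its last sample must either contribute a shorter area or be discarded, and the SAP does not say which. A paired t-test also discards participants with one visit and leaves any period effect in the error term.

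The AUC has standing as an outcome: one protocol section makes it primary, and the SAP calls these analyses confirmatory. Truncated areas add noise, and they add bias if late samples are lost more often in one condition. Discarded pairs cost power. If completers are unequal by order, part of any period effect enters the treatment difference.

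**Working it through.** **Inputs from the documents.** Mean 8.6 and SD 2.3 mmol/L, 15% reduction, r = 0.7, N = 20, samples at 0, 30, 60, 90, 120, 150 and 180 minutes, two-sided 0.05 (SAP, sample size, primary endpoint and reporting sections).

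**The plan's own figure.** Effect = 0.15 × 8.6 = 1.29 mmol/L. SD of the paired difference = 2.3 × √(2 × (1 − 0.7)) = 1.782. Standardised effect = 1.29 / 1.782 = 0.724, close to the stated 0.73. At 0.73 the exact paired t-test gives n = 14 one-sided (power 0.826) and n = 17 two-sided. The stated 14 is therefore matched one-sided. That is a separate point, and 20 covers both.

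**Truncation, one visit, flat profile at 8.6.**

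- Full total AUC: 8.6 × 180 = 1548 mmol/L·min. Planned effect: 0.15 × 1548 = 232.
- Without the 180-minute sample: 8.6 × 150 = 1290, a loss of 258 (16.7%).
- At the planned ketone level, 8.6 − 1.29 = 7.31, the loss is 30 × 7.31 = 219.
- One missing sample between 30 and 150 minutes costs nothing on a flat or linear profile, because the trapezoid bridges it.

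**Truncation, mean of 20 pairs.** Each truncated visit moves the mean difference by 258 / 20 = 12.9, and 12.9 / 232 = 5.6% of the planned effect. With no true effect and four truncated visits all in one condition, simulated type I error is about 0.09. If the four are spread at random it stays near 0.05.

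**Power for total AUC under assumed missingness.** The within-visit noise SD of 0.4 and the missingness rates are assumptions. The effect is 1.29 mmol/L from 30 minutes on and zero at time 0.

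- Area effect: 1.29 × (5 × 30 + 15) = 1.29 × 165 = 212.9.
- SD of the area difference: the between-visit part is 1.782 × 180 = 320.7. The noise part is √2 × 0.4 × √(5 × 30² + 2 × 15²) = 39.8. Together √(320.7² + 39.8²) = 323.2.
- Standardised effect: 212.9 / 323.2 = 0.659, which at n = 20 gives power of about 0.80 with complete data.

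| Assumed loss | Truncated | Time-weighted | Incomplete pairs dropped |
|---|---|---|---|
| 10% of post-dose samples | 0.74 | 0.79 | 0.24 |
| 20% of 180-minute samples | 0.73 | 0.79 | 0.57 |

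These are simulated values; a repeat of 3,000 runs agreed within about 0.02. In the last column, the expected number of complete pairs is 20 × 0.9¹² = 5.6 in the first row and 20 × 0.8² = 12.8 in the second.

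**One-visit participants.** At a standardised effect of 0.73, two-sided power is 0.872 with 20 pairs, 0.831 with 18 and 0.779 with 16.

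**Period.** With balanced order, an unmodelled period effect p inflates the SE by √(1 + (p / 1.782)²). For p = 0.25, 0.5 and 1.0 mmol/L (assumed) this is 1%, 4% and 15%. In the complete-data case above, p = 1.0 lowers power from 0.80 to about 0.70. Bias is p × (n₁ − n₂) / n, which is zero when completers are balanced. With an illustrative 11 and 7 it is p × 4 / 18, or 22% of p.

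**The case against.** The strongest reply is that the primary mixed model already deals with incomplete profiles, one-visit participants and period. The t-tests are additional, and the SAP's wording describes them as exploring the endpoint as well as confirming it. This stands: the primary analysis is not impaired. It does not remove the point, because analysis 4 is the only SAP analysis of the quantity that the protocol's design section names as primary.

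A reader might infer several stronger things that the documents do not support:

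- *That the SAP prescribes truncation.* It does not. It bars imputation and defines both areas over 180 minutes, so treating an incomplete AUC as missing is at least as natural a reading. That reading loses pairs instead, and in the assumed cases it costs more power.
- *That truncation outweighs the planned effect.* The 258 is one visit's loss and the 232 is a mean treatment difference. Per truncated visit the mean shifts by 5.6% of the planned effect. Even the single-visit figure needs a roughly flat curve and a missing last sample. It does not carry over to peak or incremental AUC: for a fall of 1.29 mmol/L reached by 60 minutes, net incremental AUC loses 30 × 1.29 = 39.
- *That the SAP contradicts itself over one-visit participants.* Its statement that they can be included is about the model, so there is no contradiction.
- *That omitting period biases the tests.* The protocol balances order, so bias needs unequal completers. Otherwise the cost is precision, and it is small for period effects up to 0.5 mmol/L.

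**Conclusion.** The point holds for analyses 1 to 4 only. They are paired t-tests without period adjustment, they drop participants with one condition, and the no-imputation rule forces an unstated choice between truncating and discarding incomplete visits. Neither choice is harmless under the assumed losses: total AUC power falls from 0.80 to 0.73–0.74 with truncation, and to 0.24–0.57 when incomplete pairs are dropped. Using all observed time, as in the time-weighted column, keeps about 0.79. Ignoring period costs 1% to 15% in SE over the assumed range.

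The power figures rest on assumed missingness, the assumed within-visit noise and an effect that starts by 30 minutes. The documents report no counts of missing samples or dropouts. If nearly all samples and visits are complete, little is lost. This is a change that should be made to supporting analyses, not a flaw in the primary model.

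**What to change.** **Total AUC (analysis 4).** Estimate the treatment difference as the trapezoid-weighted sum of the mixed model's condition differences: weight 30 minutes at each of 30 to 150, and 15 at 180. The time-0 difference is taken as zero because the model adjusts for baseline, and the SAP should say so. Code period as visit 1 or 2. This uses every observed post-dose sample, keeps one-visit participants and adjusts for period. If the model is run on log glucose, state how the contrast is returned to the AUC scale.

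**Incremental AUC, peak and peak above baseline (analyses 1 to 3).** Replace the paired t-test by a period-adjusted crossover test, in which the within-person difference is regressed on order. State which samples a visit must have to count, including time 0 for the two baseline-referenced measures. Report how many visits are excluded, by condition.

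**Cost.** SAP wording and a few lines of R, one degree of freedom for order, and a description slightly less simple than a paired t-test. Analyses 1 to 3 will still lose visits that lack the required samples.
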